4.6 TRIAL SAFETY ASSESSMENTS

This is a low risk trial, and no serious adverse events are anticipated. However, it is possible that there may be allergic reactions to the Twinblocks and this will be recorded as an expected adverse event in the CRF. The Twinblock appliance treatment will be discontinued in case of allergic reaction and discontinued from the trial and other options for management of the increased overjet will be provided. The site PI will report any SAE that is both related to the research procedures and is unexpected to the CI and the CI will send an NRES Safety Report to the appropriate REC within 15 days of becoming aware of the event. A copy of the Report will be sent in parallel to the Sponsor. An annual progress report will be submitted to the appropriate REC and a copy of the Report will be sent in parallel to the Sponsor.

Consideration and potential impact of the trial following the peak of the COVID-19 pandemic have been mitigated to ensure safety of participants and staff. The visits for treatment during the trial will be part of routine non aerosol generating dental care, with physical access to the dental hospital/orthodontic practice complying with Scottish government restrictions on social distancing. This information will be provided to participant and parent/carer prior to attendance and suitably prepared ahead of their appointment so that total contact time spent in the dental hospital/ orthodontic practice is reduced. Covid-19 screening will be undertaken ahead of the visit where possible and a high level of hand hygiene will be adopted with the provision of antiseptic hand gel on entrance and exit. To reduce contamination, minimised wait times in common areas will be adopted and safe entry/exit will be ensured with appropriate signage. Face coverings will be required to be worn where indicated by Scottish government guidance.

Radiographs are part of routine clinical investigations. Effective Dose per lateral cephalogram - 0.004mSv (from HPA-CRCE-012 'Frequency and Collective Dose for Medical and Dental X-Ray Examinations in the UK, 2008'). As the patients in this study are 9-14 years old, the risk is age corrected to 11% per Sv. The combined risk of cancer mortality from both exposures in this study is of the order of 1 in 1.1 million

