Vectra® H1 handheld 3D camera will be used to record the patient's three-dimensional (3D) facial characteristics, allowing quantification of 3D soft tissue volume changes. The camera works like any other and would require three facial captures which are automatically stitched into one 3D image with the provided software. The whole process will take 10 minutes. The need for 3D quantification of the soft-tissue effects of functional appliances has been highlighted (Flores-Mir 2006). The immediate soft tissue effects, especially of the soft tissue chin (Sharma 2005) have been shown to be only 40% of the predicted outcome (Salloum 2018). Landmarking of the pre- and post-treatment 3D images will be done using the VAM (Vectra Analysis Module) software and superimposed to measure the difference in linear distance in millimetres.

Lateral Cephalogram

Cephalometric radiographs are routinely taken as part of assessment and planning for orthodontic treatment. Modern digital lateral cephalometric radiographs are very low dose. It is used to assess whether the aetiology of malocclusion is due to skeletal relationship, dental relationship or both and quantify treatment changes. The radiographs will be taken at baseline, end of twinblock treatment and towards end (near end) of fixed appliance treatment in accordance with normal clinical practice. Eastman cephalometric analysis (Mills, 1982) will be done on the radiographs to assess the skeletal and dental changes associated with both the groups. The analysis will include angles SNA (sells-nasion-point A), SNB (sella-nasion-point B), ANB (difference between SNA and SNB), upper incisor long axis to maxillary plane (anterior nasal spine -posterior nasal spine), lower incisor to mandibular plane (gonion-menton), MMPA (maxillary-mandibular plane) and linear measurements - facial proportion (ratio of lower face height to total anterior face height) and APog (tip of lower incisor form line connecting point A-Pogonion)

Patient Experience questionnaire

This validated questionnaire, based on the three-questionnaire approach, will evaluate patients perception of their malocclusion pretreatment (T0) and patients' experience with wearing the fixed and removable Twinblock appliances 3 months into treatment (T1) and at the end of Twinblock phase of treatment (T4).

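### The radiation risk in section 4.6 counts two lateral cephalograms, but the protocol schedules three; if all three count, the stated risk is about one third too low

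*Protocol*

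**What the plan says.** Section 4.6 (Trial Safety Assessments) gives both inputs and the result in one short paragraph.

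- Dose: "Effective Dose per lateral cephalogram - 0.004mSv".
- Risk coefficient: "As the patients in this study are 9-14 years old, the risk is age corrected to 11% per Sv".
- Result: "The combined risk of cancer mortality from both exposures in this study is of the order of 1 in 1.1 million".

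The same paragraph introduces the films with the remark "Radiographs are part of routine clinical investigations".

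The schedule is given elsewhere.

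- Section 6.1, under Lateral Cephalogram: "The radiographs will be taken at baseline, end of twinblock treatment and towards end (near end) of fixed appliance treatment".
- The data collection table in section 4 (the trial matrix) ticks the lateral cephalogram at T0, T4 and T5, with a note that the last is taken near the end.
- Table 2 in section 3.2.2 lists T0, T4 and T5 for the objective that includes cephalometric analysis.

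**The concern.** The word *both* in section 4.6 means two exposures, whereas the schedule has three. Either the risk was worked out for a different schedule from the one now in the protocol, or one film was left out on purpose and the text does not say so. In both cases a reader of section 4.6 cannot tell which exposures the figure covers.

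This is the only numerical estimate of participant risk in the protocol, and it concerns children aged 9 to 14. The protocol goes to a research ethics committee for a favourable opinion, so a stated radiation risk should match the exposures that the same document schedules. No efficacy result, sample size or analysis depends on the figure. What is at stake is the accuracy of a safety statement.

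**Working it through.** **Inputs**

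- Dose per film, d = 0.004 mSv = 4.0 × 10⁻⁶ Sv (section 4.6).
- Risk coefficient, r = 11% per Sv = 0.11 per Sv (section 4.6).
- Number of films, k: two by the wording of section 4.6; three by section 6.1 and the data collection table.

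**Formula**

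Combined risk = k × d × r. Risk per film = 4.0 × 10⁻⁶ × 0.11 = 4.4 × 10⁻⁷.

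**Reproducing the stated figure**

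| Films (k) | Combined risk | Expressed as 1 in |
|---|---|---|
| 1 | 4.4 × 10⁻⁷ | 2.27 million |
| 2 | 8.8 × 10⁻⁷ | 1.14 million |
| 3 | 1.32 × 10⁻⁶ | 0.76 million (757,576) |
| 4 | 1.76 × 10⁻⁶ | 0.57 million |

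Only k = 2 rounds to 1 in 1.1 million. Working backwards, (1 / 1,100,000) / (4.4 × 10⁻⁷) = 2.07 films. If 1.1 million is a rounding of anything from 1.05 to 1.15 million, the implied count runs from 2.16 down to 1.98. The figure was therefore worked out for two films, and *both* is not loose wording.

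**Size of the discrepancy if all three films count**

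- Three films against two: 1.32 × 10⁻⁶ / 8.8 × 10⁻⁷ = 1.5, so the three-film risk is half as much again.
- Shortfall of the two-film figure: 1 − 2/3 = 33%.
- Shortfall of the rounded 1 in 1.1 million: 1 − (1 / 1,100,000) / (1.32 × 10⁻⁶) = 31%.

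**Absolute size**

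The difference is 1.32 × 10⁻⁶ − 0.88 × 10⁻⁶ = 0.44 per million per child. Over the 88 planned participants that is 88 × 0.44 × 10⁻⁶ = about 0.00004 expected events.

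**The case against.** **The baseline film may have been left out deliberately.** It is a planning film, and the two exposures might be those taken after treatment starts. This reading cannot be excluded, but the protocol does not state it. Section 4.6 calls radiographs in general routine, and section 6.1 describes all three together as following usual practice. Routine status therefore does not separate the baseline film from the other two. T0 is also a listed data collection point for the cephalogram. What stands is that the right correction may be to name the films counted instead of changing the number.

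**The wording is hedged and the risk is tiny.** The protocol says the risk is of the order of the value given, and 1 in 1.1 million and 1 in 0.76 million are close on any practical scale. This bears on importance and is accepted. It does not turn two exposures into three, and a figure given to two significant digits should match the schedule beside it.

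**Table 2 is weak support.** Its T0, T4, T5 entry is shared by cephalometric analysis, facial volumes and 3D scans. That is fair. The film-specific evidence is section 6.1 and the data collection table, and Table 2 merely agrees with them.

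**Stronger readings that the documents do not support.**

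- A reader might take the 50% excess to mean that the risk is understated by half. It is not: the stated value is two thirds of the three-film value, and an understatement by half would need four films.
- A reader might infer that the trial exposes children to unsafe or additional radiation. The protocol describes all the films as normal practice, and the risk is very small under either count.
- A reader might assume that families have relied on this figure. The participant documents are not available, so that cannot be said.

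**Conclusion.** The point holds as an internal inconsistency. The combined risk in section 4.6 is a two-film figure, while section 6.1 and the data collection table each schedule three films, with Table 2 consistent. No text says that a film is excluded from the count.

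If all three films count, the protocol's own inputs give about 1 in 760,000, and the stated risk is about one third too low. This rests on taking the 0.004 mSv dose and the 11% per Sv coefficient as given, neither of which was checked against an outside source, and on adding the risk of each film linearly, as the protocol's own figure does. If the sponsor meant to count only two of the three films, the number can stand, but the text must identify them.

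The matter is minor: the arithmetic is certain, but the consequence is confined to one safety sentence.

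**What to change.** Reconcile the number of exposures in section 4.6 with section 6.1, the data collection table and Table 2. Then do one of two things:

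- restate the combined risk for every film scheduled, which for three films on the protocol's own inputs is about 1 in 760,000; or
- keep the two-film figure and state which film is excluded from the count and why.

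In either case, replace *both exposures* with the explicit number and timepoints of the films counted. Use the same figure in any other trial document that quotes it. Nothing here bears on how many films should be taken; that is for the sponsor and the clinical team.

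The cost is one corrected sentence, which can go in with the next amendment. If all three films are counted, the stated risk becomes slightly less favourable. No change to the design, sample size or analysis follows.

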4.6.1 Potential Risks

If there is a problem with the fixed or removable Twinblock, the patient may need to make an additional appointment for advice/assistance/repair. The participant will be compensated for any additional visits due to breakage of blocks with a £10 voucher.

4.7 INCIDENTAL FINDINGS

Any incidental findings previously undiagnosed condition) considered to be clinically significant will be reported to the participant's GP by the Site PI, with the consent of the participant.

4.8 TRIAL POPULATION

Patients will be recruited from NHS primary care orthodontic practices and secondary care orthodontic units in Tayside (Dundee) and Grampian (Aberdeen) region.

4.9 NUMBER OF PARTICIPANTS

We plan to undertake a multicentre randomised clinical trial in Tayside (primary and secondary care) and Grampian (primary care) regions as a two-arm parallel design of fixed and removable Twinblock appliance for overjet reduction. To detect a clinical important difference, 26 participants per arm, giving a total of 52 are required to complete the trial. With the long nature of treatment and high levels of drop out, combined with missing data from non-treatment visits, it was decided to allow for 40% drop out or incomplete data collection and therefore 88 patients will be recruited, 44 to each arm of the trial. The recruitment is anticipated to take around 18-months to complete.

4.10 INCLUSION CRITERIA

- Class II division 1 malocclusion
- No history of active orthodontic treatment
- Overjet > 6mm (IOTN 4a/5a)
- Age 9-14 years
- Child & parent/carer who are able to assent and consent, respectively

4.11 EXCLUSION CRITERIA

- Overjet <6mm
- Mobile/loose deciduous teeth,
- Profound hypodontia affecting the incisor region (>1 missing tooth per quadrant)
- Subjects taking growth hormone or endocrine disorders
- Suspected or identifiable syndromes
- Subjects with cleft lip and palate
- Anterior open bite

5 PARTICIPANT SELECTION AND ENROLMENT

5.1 IDENTIFYING PARTICIPANTS

All patients referred to the recruiting centres (Dundee Dental Hospital, Beam Orthodontics (Dundee), Perla Orthodontics (Dundee) and The Orthodontic Clinic (Aberdeen)) for orthodontic treatment, attend for initial assessment. At this initial assessment, the treating orthodontist (local PI) and/or a delegated member of the clinical team will identify those patients who appear to meet inclusion criteria. A suitably trained member of the local clinical team will then explain to them the trial, provide written information, and invite them to participate.

5.2 CONSENTING PARTICIPANTS

Identified patients will be invited to participate in the trial by the site PI or one of the delegated member of the clinical team trained in taking informed consent, who will be a registered practitioner with the General Dental Council (GDC). The study will be discussed with parents/guardians and potentially eligible children. Participants and parent / carers will be given the opportunity to ask questions and appropriate consent/assent forms will be completed. This would be at the next appointment (4-6 weeks) to allow for time for patients'/parents' to process the information. Where a parent/carer/ or participant requests to speak with a member from the trial team the consent process will not be completed until the parent/carer or participant has spoken to the team member and had all their questions answered to their satisfaction.

As age of legal capacity says patients can consent from 12yrs for dental care if they have capacity, therefore for patients aged 09-11 years, child assent and parental consent forms will

be completed. For children aged 12-14 years old, participant consent and parental assent forms will be completed.

5.3 SCREENING FOR ELIGIBILITY

Screening will be done by the PI from the initial records (impressions or intra-oral scan) collected. Confirmation of eligibility will be given by the chief investigator on viewing clinical records.

5.4 INELIGIBLE AND NON-RECRUITED PARTICIPANTS

Patients who are screened and found to be ineligible will have normal care provided as per normal clinical protocols. Similarly, patients identified who decline to participate will enter treatment as per normal clinical protocols.

5.5 RANDOMISATION

5.5.1 Randomisation

Randomisation will be stratified by gender, overjet measurement (IOTN 4a or 5a) and site, using the on-line TCTU (TRuST – Tayside Randomisation System) randomisation system. TCTU's Randomisation System (TRuST) provides GCP compliant web-based randomisation to produce balanced randomisation allocation based on a minimisation with stratification algorithm.

The system has been built to deal with each combination of variables by making up a block, which is how the participants are stratified across at point of randomisation. However, to make it more difficult to predict the allocation it uses random block sizes. Therefore, over time it will keep the variable balanced, with an automatic notification from the system to stop recruiting to a particular group.

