Functional appliances are frequently used for the treatment of Class II division 1 malocclusion by harnessing the muscular forces to move the teeth and the jaws. The American Dental Association describes them as "loose, usually removable intra-oral devices which alter the muscle forces against the teeth and craniofacial skeleton. These are dynamic appliances, which depend on altered neuromuscular action to effect bony growth and occlusal development. They are usually used in mixed dentition to treat pediatric malocclusions" (Glossary of American Dental Association, 1992). As such, functional appliances (and other growth modification techniques) straddle the comprehensive and camouflage categories. Due to the growth potential in younger patients, the skeletal response to treatment can be greater than with adolescent patients. In many cases with a substantial overjet (i.e. Index of Orthodontic Treatment Need categories 4 and 5), a Class I skeletal relationship can be produced at the end of treatment, particularly where a retrusive mandible is a key presenting feature. In adolescent patients the skeletal response is reduced with most of the occlusal change resulting from dentoalveolar compensation. Although the age at treatment has not been shown to influence the amount of skeletal change delivered by functional appliances in a single randomised controlled trial (O'Brien et al, 2009), a favourable vector and magnitude of growth underpins cases that are successful with orthodontic growth modification (Tulloch et al, 2004) and it is logical to harness this where possible.

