However, like all removable functional appliances, compliance with the removable Twinblock appliance can be problematic. The issue with compliance has been quantified by Parekh et al (2019) for the Twinblock appliance at mean daily wear of 12.38 hours or 51.6% of that recommended. Furthermore, age is also a factor in compliance with O'Brien et al. (2003c) finding older patients had unusually high failure rates (34%) compared to younger patients (O'Brien et al. 2003a) at 19%. The solution to the problem of compliance is to use a fixed functional appliance. The oldest known fixed functional appliance is the Herbst appliance which was first described at the start of the 20th century and re-introduced by Hans Pancherz more recently. It is comprised of two maxillary and mandibular sections – either cast or banded. However, problems include breakages, regular re-cementing of the appliance, and patient acceptance. The most recent version of the Herbst appliance was used in the UK MRC-funded multicentre RCT (O'Brien et al. 2003c) comparing the removable Twinblock appliance with the Herbst. The rate of failure during the functional phase was surprisingly high in the Twinblock group at 34%, and much lower in the Herbst group at 13%.

Combining the extensive research literature on the Herbst appliance with clinical experience produces the following summary:

- The Herbst appliance reduces almost all overjets in 6 months which compares to an average of nine months with the removable Twinblock appliance
- Patients find the Herbst appliance not excessively intrusive after the first week like the removable Twinblock appliance
- There is an inconveniently high rate of decementation, mechanical failure and lower incisor proclination with the Herbst appliance
- A functional appliance that can be rapidly and reliably added to a conventional fixed appliance will probably prove very popular.

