8 STATISTICS AND DATA ANALYSIS

8.1 SAMPLE SIZE CALCULATION

The feasibility study conducted by us in Dundee Dental Hospital (REC 17/ES/0126) has produced a clear route of progression (NIHR criteria) to the substantive multicentre RCT by estimating all the important parameters. Using initial data obtained from our feasibility study, for an effect size of 0.80 (difference of 81 days and SD 101 days), an alpha value of .05 and a power of 80% the required sample size was computed as 26 participants per group giving a total of 52. This is a assuming a simple independent t-test analysis and utilising sample size software PASS20. Recruitment will be across 4 sites and so randomisation will be stratified by site. With the long nature of treatment and high levels of drop out, combined with missing data from non-treatment visits we decided to allow for 40% drop out or incomplete data collection and therefore 88 patients will be recruited, 44 to each arm of the trial.

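### The protocol names age as a factor in Twinblock compliance but uses it neither in allocation nor in the stated primary model; adding baseline age as a covariate is a small, nearly free gain

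*Protocol*

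**What the plan says.** Section 2 (Background and rationale) introduces its failure figures with the words "age is also a factor in compliance with" and then contrasts two cited trials: "older patients had unusually high failure rates (34%) compared to younger patients", the younger group being put at 19%. It attributes variable response to functional appliances to compliance together with active growth. On skeletal effects it says "In adolescent patients the skeletal response is reduced with most of the occlusal change resulting from dentoalveolar compensation". It then adds that "the age at treatment has not been shown to influence the amount of skeletal change delivered by functional appliances", citing one randomised trial.

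Section 4.10 enrols ages 9 to 14 as one population. On allocation, section 5.5.1 states "Randomisation will be stratified by gender, overjet measurement (IOTN 4a or 5a) and site". It describes the system as "based on a minimisation with stratification algorithm" and, in the next paragraph, as forming a block for each combination of variables with random block sizes. Section 8.1 confirms four sites.

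Section 8.2 compares mm/month of overjet change between arms with a multilevel linear model. Treatment centre is the only thing the text says the model controls for. The protocol gives no reason for leaving age out of either step.

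**The concern.** Reducing compliance problems is the stated rationale for the fixed appliance (section 2.1), and age is the patient characteristic for which the protocol quotes failure rates. It quotes no treatment outcome rate by gender, yet gender is a balancing factor.

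A variable believed to be prognostic can be used in the design, in the analysis, or in both. Here it is used in neither. Two things are at stake: some precision in a small trial, and the credibility of the result if the arms happen to differ visibly in age.

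**Working it through.** **The plan's own figure.** Section 8.1 gives a difference of 81 days, SD 101 days, alpha 0.05 (two-sided assumed) and 80% power.

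- Normal approximation: n = 2 × (1.960 + 0.842)² × (101/81)² = 24.4, so 25 per arm.
- Exact t-test at d = 0.80: power is 79.1% at 25 and 80.7% at 26, so 26 per arm.
- Dropout: 26 / (1 − 0.40) = 43.3, so 44 per arm and 88 in total.

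The stated sample size is reproduced, and this point does not affect it.

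**Chance imbalance in age.** The protocol gives no age distribution. Assume half the children are older, with a range of 30% to 70%, and that age is unrelated to the existing factors. The SD of the between-arm difference in the share older is sqrt(2p(1 − p)/n).

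| Per arm | Share older | SD (points) | 95% range (points) | P(gap ≥ 10) | P(gap ≥ 20) |
|---|---|---|---|---|---|
| 44 | 50% | 10.7 | ±21 | 34% | 7% |
| 44 | 30% or 70% | 9.8 | ±19 | 29% | 5% |
| 26 | 50% | 13.9 | ±27 | 49% | 13% |

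Sections 5.5.3 and 8.3 specify intention to treat with imputation, so the 44-per-arm rows are the relevant ones. The last row describes completers only.

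**Size on the failure scale.** Suppose the quoted gap, 34 − 19 = 15 points, held in full in both arms. The shift at the 95% limit for 44 per arm is 0.209 × 15 = 3.1 points. If the gradient held only in the removable arm, it is 1.96 × sqrt(0.25/44) × 15 = 2.2 points. A 20-point imbalance shifts the failure difference by 0.20 × 15 = 3.0 points. With mean failure (34 + 19)/2 = 26.5%, the standard error is sqrt(2 × 0.265 × 0.735/44) = 9.4 points, so the shift is 0.32 SE. Type I error conditional on that imbalance is about 6.2%. Averaged over all randomisations it stays at 5%.

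**Size on the planning scale.** The protocol gives no SD for mm/month, so the planning scale of days is used. The correlation of a half-and-half age split with failure is 0.15 × 0.5 / sqrt(0.265 × 0.735) = 0.17, so R² = 2.9%. Assume the same R² for days.

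- Difference between older and younger children: 2 × 0.17 × 101 = 34 days.
- Effect of a 20-point imbalance: 0.20 × 34 = 6.9 days, or 6.9/81 = 8.5% of the target difference.
- Gain from adjustment: the effective d becomes 0.80 / sqrt(1 − 0.029) = 0.812, and power at 26 per arm rises from 80.7% to about 81.9%. The normal-approximation n falls from 24.4 to 24.4 × 0.971 = 23.7, so from 25 to 24 per arm.
- If age is unrelated to the outcome (R² = 0), both the shift and the gain are zero.

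**Age as a further stratum.** The present cells number 2 × 2 × 4 = 16, or 88/16 = 5.5 children each. A two-level age stratum makes 32, or 2.75 each.

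**The case against.** The strongest case against is that nothing here is misstated. Eligibility and allocation are consistent with each other, randomisation is valid without stratifying on age, and the 5% level already allows for chance imbalance in any covariate. That stands, and it rules out calling this a bias.

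A reader might go further and infer that the trial pools two populations with failure rates of 19% and 34%, so that an age imbalance would distort the appliance comparison. The documents do not support that:

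- The two rates come from separate trials, and section 2 gives the ages of neither. The contrast mixes age with trial, and where 9 to 14 falls relative to either group is unknown.
- Both rates concern the removable appliance. Section 2 reports 13% failure with a fixed appliance, the Herbst, alongside the 34%, so the age gradient need not carry over to the fixed arm.
- The evidence on age and skeletal change is mixed within section 2 itself.
- Failure is not a listed outcome. The primary outcome is mm/month, and no document links it to age in figures.

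It can also be said that covariates belong in a statistical analysis plan, which is not shown and may include age. That is fair, and it limits the weight of the point. It does not remove it, because section 8.2 already describes the primary model and what it controls for, and that description leaves out a factor the protocol itself calls relevant.

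**Conclusion.** The point holds as a minor one. The protocol treats age as prognostic in its rationale and then uses it in neither allocation nor the stated primary model. The comparison remains unbiased and overall type I error stays at 5%. The cost is a little precision and some exposure to a visible chance imbalance.

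On the assumptions above (half the children older, R² of 2.9% carried from failure to the planning outcome), a 20-point imbalance arises in about 7% of randomisations at 44 per arm and moves the estimate by about 7 of 81 days. Adjustment is worth about one percentage point of power. Both figures shrink towards zero if age matters less than the quoted contrast suggests.

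**What to change.** In section 8.2, state that the primary multilevel model includes baseline age as a continuous covariate alongside treatment and centre, fixed before the data are seen. The bootstrapped t-test fallback in that section takes no covariates, so the text should also say whether age is dropped there. If a statistical analysis plan already includes age, a cross-reference is enough.

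Do not add age as a further blocked stratum. If the system runs blocks in every combination, as one paragraph of 5.5.1 describes, cells of about 2.75 children would leave many blocks incomplete and could weaken balance on the existing factors. A covariate avoids this and can still be specified if recruitment has begun.

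The cost is one sentence and one model parameter. Age is already needed for eligibility, and the sample size does not change.
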